## **VII. Data and Safety Monitoring Plan**

Ongoing safety monitoring will be performed by the study staff, including the Principal Investigator (PI) and co-investigators. The PI will have ultimate responsibility of assuring patient safety. Safety issues will also be addressed in the annual reports to Beaumont's Investigational Review Board (IRB).

Additional data safety monitoring procedures include:

- Research Administration's Clinical Research Quality and Process Improvement Program (CRQIP) will perform in-house monitoring of the first patient enrolled after the completion of visit 1
- An audit of the study records after the first 10 patients are enrolled and at the half way point of enrollment by an RN in the Urology Research Department that is not directly involved with the research study. This will be done to ensure the safety of subjects and lack of significant adverse effects.

As an on-going plan, any adverse effects occurring during the treatment phase and determined to be related, potentially related, possibly related, or probable to the study treatment (prolonged irritation, hemodynamic changes, significant pain, or other deemed significant by clinicians) will be reported to the research nurse and then to the PI at the time of the event. Adverse events,

Percutaneous Tibial Nerve Stimulation (PTNS) therapy for female patients suffering from  
Multiple Sclerosis

serious adverse events, and unanticipated problems not listed in the risks section of this protocol will be reported per IRB guidelines.

Subject records will be reviewed to verify case report form (CRF) completion and delinquencies, and capture protocol deviations and frequency of unanticipated problems/adverse events. To identify, evaluate, and prevent adverse events, the total number of events will be reviewed, as well as the details of each event, including visit number and severity. Data will be reviewed to identify trends and possible concerns. Enrollment data will direct recruitment efforts and assist in study planning.

The overall objectives of routine monitoring are to:

- Document clinical study progress.
- Document that the protocol and associated forms are current.
- Obtain and review current clinical data, reports, and source documents.
- Review the overall study status including verification of the study files. All required documents and records should be accurate, complete, and current.
- Confirm that all subjects have signed the informed consent form.
- Confirm that all enrolled subjects have met the eligibility criteria.
- Verify accuracy of transferring data from source document(s) to the CRFs to the database.
- Confirm complete, accurate, and timely event reporting.
- Confirm adequacy of staff and facilities.
- Review communication records.
- Verify identification and reporting of protocol violations.

Outcomes of all scheduled and unscheduled study monitoring will be documented. Follow-up action items will be included in the report. The monitoring summary report will be forwarded to the PI and research coordinator.

#### **Quality Control and Quality Assurance (QC/QA)**

The PI or designee has primary responsibility for QC/QA activities of the data. Beaumont's Research Institute also audits investigator-initiated studies to ensure compliance with consent processes and reporting requirements. The key QC/QA activities for the study will be:

- Clearly formatted and carefully constructed CRF;
- Sign-Off Procedures for all CRFs;
- Verification of subject eligibility at each visit

A database will be created utilizing RedCap, MS Excel, or equivalent software. Only designated study personnel will have access to the database, which will be stored on the Urology Research Department's shared drive. Access to the computerized system will be password protected. To ensure accuracy of data entry, database entries will be cross-checked against source documents. The shared drive is backed up nightly to ensure minimal data loss, even in the most catastrophic system failure. The database will be active until all study visits are completed, final monitoring activities have been conducted, and all data queries have been resolved. After that time, the database will be locked, prohibiting any changes to the data.

**Percutaneous Tibial Nerve Stimulation (PTNS) therapy for female patients suffering from  
Multiple Sclerosis**

All study records, including both paper and electronic, will be stored in accordance with all federal and institutional requirements, including, but not limited to, the HIPAA Privacy Rule, the Food and Drug Act, and Medicare policy. The stored data will be kept in a secure, protected manner. All records will be retained, at a minimum, for eleven years beyond study completion.

### **VIII. Adverse events and serious adverse events**

- AEs will be collected and reported from the start of study treatment, visit 1 until completion of the participant's last study-related procedure, which may include final follow-up. SAEs related to study procedures will be collected from the time of participant began study treatment, at visit 1 through the final follow-up contact is completed.
- PIs are not obligated to actively seek new onset AEs or SAEs after the protocol-defined reporting period; however, if the PI learns of any SAE and he/she considers the event to be reasonably related to the study intervention or study participation, the PI must promptly notify the IRB.
- The PI will assess the severity and causality of AEs and SAEs and classify the event as Related, Probably Related, Possibly Related, Probable, or Not-related to the Study.
- The PI will provide follow-up of each AE/SAE until resolution, the condition stabilizes, the event is otherwise explained, or the participant is lost to follow-up. The PI will report all AEs and SAEs to the IRB of record, according to policy. SAEs will be reported within 24 hours of knowledge of the event.

**Unanticipated Problems (UP), include any incident, experience, or outcome which meets all three of the following criteria:**

- **Unexpected (in terms of nature, severity or frequency) given the known risks associated with the study treatment. Please refer to Section IV.**
- **Related or possibly related to participation in the research.**
- **Suggests the research places participants at a greater risk of harm than was previously known or recognized.**

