**B. Study visits:**

**Screening and Consent Visit 0: Week 0**

Eligible patients that have provided voluntary written consent, will complete the enrollment questionnaires including (demographics, medical history, concomitant medications etc.) and OAB-q-SF. If a subject needs to be discontinued from antimuscarinics/beta-3 agonists, this will be discussed after consent. The subject will discontinue the use after the time of consent for  $\geq$  2 weeks and remain off throughout study participation. Patient will need to be screened after washout period to assess if patient still meets eligibility criteria. A urinalysis via urine dipstick and pregnancy test (for women of child-bearing potential) will be performed at screening. *If the urinalysis is positive for leukocytes a urine culture will be sent. Patients with a positive urine culture may be treated per standard of care by the study physician. After treatment is completed, a repeat urine will be checked. If repeat urinalysis is negative, the subject will be allowed to complete the 3-day voiding diary and study activities.* A 3-day voiding diary and instruction will be reviewed with and dispensed to the subject to return at their next scheduled visit.

Subsequent visits that require a urinalysis and are positive for leukocytes if the patient is symptomatic, a culture will be sent per the investigator's discretion.

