### **IV. Risks and Benefits**

#### ***PTNS or Sham Treatment***

##### **Less frequent (occurring from 1% to 10% of the time):**

- Discomfort/pain/pressure/tingling at, or near, the stimulation site, or the subject's lower leg or foot
- Redness/inflammation at, or near, the stimulation site
- Possible worsening of OAB symptoms (Stimulating the nerves can either improve, worsen, or have no effect on symptoms) i.e. increased frequency, urgency, nocturia/ leaking due to the procedure

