##### **Rare (occurring less than 1% of the time):**

- Skin irritation
- Electrode burn
- Allergic reaction to adhesive pad gel
- Numbness of toes
- Allergic Reaction
- Possible increase in lower extremity pain or pelvic pain

If a patient is required to discontinue antimuscarinics/beta-3 agonists with a "washout" period to participate in the study there is a chance they may return to baseline urinary symptoms. This may include but is not limited to an increase in urinary frequency, urgency, and urinary leakage.

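### AE and SAE collection starts at Visit 1, so events in the protocol-required drug washout are not recorded as AEs, and section VIII contradicts itself on which SAEs are in scope

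*Combined protocol and SAP*

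**What the plan says.** **Collection window (section VIII).** For AEs: "AEs will be collected and reported from the start of study treatment, visit 1 until completion" of the participant's last study-related procedure. For SAEs: "SAEs related to study procedures will be collected from the time of participant began study treatment, at visit 1", through the final follow-up contact.

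**Washout (section II, Study visits, Visit 0).** For patients on antimuscarinics or beta-3 agonists, "The subject will discontinue the use after the time of consent for" at least 2 weeks; they then stay off the drug throughout participation and are screened again after washout. Visit 1 falls within 3 weeks of Visit 0, plus or minus 3 days. Randomisation and the first treatment take place at Visit 1. A patient who turns out not to be eligible may resume medication.

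**Listed risks (section IV).** Of washout the protocol says that "there is a chance they may return to baseline urinary symptoms", with more frequency, urgency and leakage as examples. Among the PTNS and sham risks occurring 1% to 10% of the time it lists "Possible worsening of OAB symptoms".

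**SAE scope (section VIII).** Beside the sentence on procedure-related SAEs, the section has the PI grade AEs and SAEs on a causality scale that includes a not-related category, and adds: "The PI will report all AEs and SAEs to the IRB of record, according to policy".

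**Prompt reporting (section VII).** Adverse effects in the treatment phase that are "determined to be related, potentially related, possibly related, or probable to the study treatment" go to the research nurse and then to the PI at the time of the event.

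**The concern.** The washout is imposed by the study, and the protocol names it as a risk of taking part. Yet the safety record opens only after the mandatory minimum washout has passed. Two things are lost.

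First, harms of the withdrawal before Visit 1 are not recorded as AEs. For patients who wash out, fail the eligibility check and are never randomised, the text provides no AE record at any time. Their experience bears on whether the washout is acceptable in the larger trial that this pilot is meant to support.

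Second, there is no AE baseline. Worsening bladder symptoms appear in section IV both as a washout risk and as a PTNS or sham risk. If worsening began at drug withdrawal and is first logged as an AE at a treatment visit, nothing in the AE data separates the two causes.

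The SAE wording is a separate defect in the same section. Staff could follow the narrow sentence or the broad ones, and the SAE listing would differ accordingly.

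**Working it through.** The documents give no calculated figure on this point, so there is none to reproduce. The check sets the provisions side by side and then sizes the gap.

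**1. Does any provision cover consent to Visit 1?**

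| Provision | Covers the washout period? |
|---|---|
| AE and SAE window, section VIII | No: starts at Visit 1 |
| PI learns of a related SAE outside the window, section VIII | No: applies only after the reporting period |
| Unanticipated Problems, section VIII | In part: the event must be unexpected given section IV, and symptom return is listed there |
| Prompt reporting, section VII | No: treatment phase and study treatment only |
| Visit 0 and Visit 1 text, section II | No AE check before the first treatment is described |
| AE row of Table 1 | Cannot be read reliably as extracted |

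**2. Length of the gap**

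- Shortest: the 2-week minimum washout = 14 days.
- Longest: 3 weeks + 3 days = 24 days.
- Visit 1 to Visit 13: 11 weekly intervals + 1 week = 12 × 7 = 84 days (nominal).
- Share of the time from consent to Visit 13: 14/(14 + 84) = 14/98 = 14%; 24/(24 + 84) = 24/108 = 22%.
- For a sham patient who goes on to open-label treatment, about 84 more days: 14/182 = 8%; 24/192 = 13%.

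**3. Effect of one misattributed event**

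With 17 per arm, one event moves an arm's rate by 1/17 = 5.9 percentage points. If the 1% to 10% range applies to worsening symptoms alone, the expected number of patients per arm is 17 × 0.01 = 0.17 to 17 × 0.10 = 1.7. A single misattributed event is thus of the same order as the rate being estimated.

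**4. Effect on active versus sham**

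Washout precedes 1:1 randomisation and applies equally to both arms, so by design it favours neither. Two calculations illustrate what chance leaves, with n = 17 per arm and b(x) = C(17,x) p^x (1−p)^(17−x).

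- *Same washout-related event rate p in both arms.* The chance that Fisher's exact test gives two-sided P ≤ 0.05 (an assumed level) is the sum of b(i)b(j) over the significant tables:

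| Assumed p | 5% | 10% | 20% | 30% |
|---|---|---|---|---|
| False arm difference | 0.1% | 0.8% | 1.9% | 2.0% |

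- *Imbalance in washed-out patients.* The chance that the arms differ by 4 or more is the sum of b(i)b(j) over |i − j| ≥ 4, with p now the share needing washout:

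| Assumed p | 20% | 30% | 50% | 70% |
|---|---|---|---|---|
| Difference of 4 or more | 13% | 19% | 23% | 19% |

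Chance imbalance is therefore plausible, and randomisation is not stratified by washout, but there is no systematic bias.

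**5. SAE scope**

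"SAEs related to study procedures will be collected from the time of participant began study treatment" restricts what is collected. A not-related category for SAEs, and a duty to report all of them, presuppose that unrelated SAEs are collected. Both cannot hold as written.

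**The case against.** The strongest reply is that the main washout harm, worse bladder symptoms, is measured before treatment. The 3-day diary is dispensed at Visit 0 and collected at Visit 1, patients are screened again after washout, and at least 8 voids per day on the diary is an entry criterion. This stands in part: there is a pre-treatment record of voiding. But the diary is an efficacy instrument. It does not record non-urinary events or date the onset of worsening, and its three days are not expressly tied to the end of washout.

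It is also right that withdrawal effects arising after Visit 1 are collected, since patients stay off drug and AEs are assessed at every treatment visit in both arms. The 14% to 22% is calendar time in a subset, not a proportion of harm missed.

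Three stronger readings are tempting, and the documents support none of them:

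- *Washout biases active against sham.* It precedes randomisation, so only chance imbalance remains.
- *Section VII lets only pre-judged related events reach the PI, with staff who know the arm doing the filtering, so the not-related category would stay empty.* Section VII sets prompt reporting of related effects. It does not say that only those reach the PI, nor who makes that first judgement; it also calls for review of the total number and details of events. Section VIII collects AEs without a relatedness limit and assigns causality to the PI.
- *Unrelated SAEs are excluded outright.* One sentence says so and others in the same section say otherwise. The finding is a contradiction, not a clear related-only rule.

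**Conclusion.** The concern holds in two respects. First, events between consent and Visit 1 are not captured as AEs, for 14 to about 24 days in each patient who washes out, including those never randomised. The Unanticipated Problems route narrows this gap but does not close it. Second, section VIII is inconsistent on SAE scope.

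The consequence is limited to incomplete safety capture and possible misattribution of an individual event or a within-arm rate, at 5.9 percentage points per event in an arm of 17. Sample size and the efficacy analysis are unaffected. How many patients are involved cannot be stated, because the documents do not give the share needing washout. The day counts assume that the drug is stopped at about the time of consent and that visits follow the stated windows; the chance calculations rest on the assumed rates shown. This is a low-cost improvement worth making, not a flaw in the trial's main comparison.

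**What to change.** 1. **Section VIII, window and scope.** Replace the two collection sentences with, for example: *AEs and all SAEs, regardless of relationship, will be collected from signed consent (Visit 0) through the last study procedure; the PI then assigns causality.* This also removes the conflict with the reporting sentence and the not-related category.
2. **Visit 1 and Table 1.** Add one AE query before the first treatment, asked before the eligibility decision so that patients who wash out and fail are included.
3. **Case report form and tables.** Flag each event's onset as before or after the first treatment and tabulate the two separately.
4. **Section VII.** State that the prompt-reporting rule for related effects does not limit which events are recorded and sent to the PI.

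The cost is wording in two sections, one query and one data field. The downside is slightly more AE entries, including events in patients who are never randomised.

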**Unanticipated Problems will be reported per IRB policy.**

### **VIV. Summarize Existing Study Data**

The use of PTNS in the neuromodulation of MS-related OAB has only been explored in small case studies but has demonstrated safety and efficacy. PTNS and SNM seem to be effective and safe therapeutic options for treating lower urinary tract symptoms in MS patients principally in case of overactive bladder (OAB) symptoms. Given their safety and efficacy, stimulations such as PTNS could be considered as a first-line treatment for OAB in MS patients, also considering that they are often preferred by patients to other commonly used treatments. Long-term sustained therapeutic effects of PTNS in MS patients were shown in a study with 21 patients (5 men and 16 women) with MS and PTNS treatment. In this study, a year of PTNS treatment with a tapering protocol of 6, 9 and 12 months of therapy was applied. A total of 21 patients were enrolled in the study. The results showed a significant improvement in frequency, urgency, nocturia, urge incontinence and voided volume at 6, 9, and 12 months when compared to baseline. Pacini et al, investigated using PTNS in MS patients with neurogenic overactive

Percutaneous Tibial Nerve Stimulation (PTNS) therapy for female patients suffering from  
Multiple Sclerosis

bladder. Patients were evaluated using voiding diaries and questionnaires after receiving 12, 30-minute sessions of PTNS, performed twice a week. 21/29 subjects were considered responders, with a reduction  $\geq 50\%$  of urgency episodes. The limitation on this study was it did not include a sham group. Additional contemporary clinical outcome data is needed. The data generated by this study would provide support for a future multi-institutional, randomized prospective trial. This would be essential for PTNS to gain FDA approval for its use in MS patients, increasing options for durable and cost-effective treatment of neurogenic urinary dysfunction.

